3.4 Data collection

A structured form was designed to collect information regarding

- (1) patient's age;
- (2) gender;
- (3) type of teeth injected
- (4) type of dental treatment (filling or pulpotomy);
- (5) total amount of local anesthetics (LAs) used (ml)
- (6) duration of the analgesia effect (min)
- (7) post-op pain (after one day)
- (8) score on WB PRS after injection
- (9) score on FLACC during injection.

The Effect of Needle-free Injection System on Dental Injection Pain in Children: A Cross-over, Randomized Clinical Trial

Statistical Analysis

Post hoc power analysis was conducted for the study and the results of the comparison between the injection systems and Wong Baker scores were evaluated. According to this, with a total data set of 28 individuals, consisting of two independent groups and two dependent measurements, the power of the study was found to be 0.94 according to the G*Power 3.9.1.4 program, based on the partial eta squared (η^2) value of 0.108 obtained with a 0.05 error margin from the repeated measures ANOVA. The data were statistically analyzed using SPSS software (version 15.0, SPSS). Paired t-tests or Wilcoxon nonparametric tests were used to compare data within groups over two time periods, according to check the distribution whether normally distributed or not. The Chi-square test (X^2 -test) was also used to compare discrete random variables. Spearman's Rho correlation coefficient was used to find any relationship between two continuous variables. A p-value ≤ 0.05 was considered statistically significant.

4. Results

Total of 28 children, consisting of 18 girls (64.3%) and 10 boys (35.7%) aged 6–12 years were involved in this study. Mean age was 8.07 years with a standard deviation of 1.41 years. At the end of this study, a total of 56 injections were obtained for 28 children as NF injection (n = 28) and TM injection (n = 28).

In the study, when the distributions of the parameters (gender, type of dental treatment, type of teeth, and post-operative pain) were evaluated according to the type of injection technique, it was found that there was no statistically significant difference between the groups. (Table 1)

Table 1. Distribution of injection techniques based on evaluation parameters

Variables		Needle Free (NF) n	Traditional Method (TM) n	Total	p
Gender	Girl	18	18	36	1,000
	Boy	10	10	20	
Type of dental treatment	Filling	22	14	36	0,051
	Pulpotomy	6	14	20	
Type of teeth injected	1 st primary molar	12	7	19	0,259

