	2 nd primary molar	16	21	37	
Post-op pain (after one day)	Pain	5	7	12	0,746
	No pain	23	21	44	

*The Chi-square test (X^2 -test) was also used to compare discrete random variables.

Accordingly Table 2, in the group that received Needle-Free anesthesia in the first session and Traditional Method in the second session, the Wong-Baker scores were 4.44 ± 3.28 and 1.55 ± 0.88 , respectively. On the other hand, in the group that received Traditional Method anesthesia in the first session, the WB score was 1.68 ± 1.91 , while in the Needle-Free anesthesia group, the WB score was 2.52 ± 2.56 . In both cases, regardless of the method of anesthesia applied first, no statistically significant difference was found in the two groups. In the FLACC scores, for the Traditional Method - Needle Free group significant change was observed ($p = 0.025$) while for the Needle Free- Traditional Method group no statistically significant difference was observed ($p=0.141$). There were significant differences in the Amount of Anesthetic Solution (ml) and Duration of the Analgesia Effect (min) between the first and second visits for both injection methods, respectively as $p=0.003$ for NF-TM and $p<0.0001$ for

The Effect of Needle-free Injection System on Dental Injection Pain in Children: A Cross-over, Randomized Clinical Trial

TM-NF groups. The amount of anesthetic solution used for the 1st visit NF injection was $0,91\pm 0,48$ ml and $0,65\pm 0,30$ ml was for the 2nd visit NF injection. These amounts were statistically lower than TM injection in both visits. In the first visit, the mean duration of the analgesia effect in the NF group was 85.00 ± 39.05 min, whereas in the second visit, the mean duration for NF injection was found to be 90.26 ± 43.25 min. In the TM group, the mean anesthesia duration for the first and second visits was 140.00 ± 59.97 min and 130.00 ± 50.74 min, respectively. Regardless of the visit in which it was first applied, the duration of the analgesia effect in the NF group was found to be statistically significantly shorter than in the TM group ($p < 0,001$).

Table 2: Comparison of the 1st visit and 2nd visit measurements for continuous random variables in Needle Free-Traditional Method and Traditional Method - Needle Free

	1 st visit	2 nd visit	p
Wong Baker (WB) Scores			
Needle Free-Traditional Method	4,44±3,28	1,55±0,88	0,056
Traditional Method - Needle Free	1,68±1,91	2,52±2,56	0,119
FLAAC			

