According to Spearman's Rho correlation coefficient test, no correlation was found between age and Wong Baker, FLACC scores, and the amount of anesthetic solution administered respectively ($p=0,830$, $p=0,436$, $p=0,976$). Similarly, no correlation was found between Wong Baker scores and the amount of anesthetic solution administered ($p=0,537$) and Wong Baker scores and the duration of the analgesia effect ($p=0,468$). However, a negative correlation was found between the FLACC score and the amount of anesthetic solution ($p=0,033$). Moreover a positive correlation was found between the FLACC score and Wong Baker scores as well as between the amount of dose administered and duration of analgesia effect respectively ($p=0,000$, $p=0,009$).

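### With one p≤0.05 rule and no named primary outcome, the pain question is split over four within-sequence tests whose significance labels disagree although all point the same way

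*Combined protocol and SAP*

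**What the plan says.** The decision rule in the Statistical Analysis part of section 3.4 is "A p-value ≤ 0.05 was considered statistically significant". No order of testing and no adjustment is given. Outcomes appear as items of one list ("A structured form was designed to collect information regarding"), none marked as primary. The only hint of a lead outcome is the post hoc power statement, where "the results of the comparison between the injection systems and Wong Baker scores were evaluated".

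The technique comparison is made inside each sequence group: "Paired t-tests or Wilcoxon nonparametric tests were used to compare data within groups over two time periods". Table 2 therefore gives two p-values per outcome. For Wong-Baker both are reported as non-significant (0.056 and 0.119). For FLACC, the Results say that "for the Traditional Method - Needle Free group significant change was observed" (p=0.025), and report no significant difference in the other sequence (p=0.141).

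The same rule is used for the subgroup tests in Tables 3 to 5 and for eight Spearman correlations, where "a negative correlation was found between the FLACC score and the amount of anesthetic solution" (p=0.033) is reported among the findings.

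**The concern.** The title question is whether the needle-free system changes injection pain. Four tests address it, they carry different labels, and nothing says which one decides. A reader can cite the Wong-Baker rows for no difference or one FLACC row for a difference, from the same paragraph.

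Two things are at stake. First, the main answer: the split by sequence may hide a consistent technique effect that a cross-over analysis would show. Second, the secondary claims: under a flat 5% rule, subgroup and correlation results are reported with the same standing as the main comparison.

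**Working it through.** **Plan's own figure.** The power statement uses "with a total data set of 28 individuals, consisting of two independent groups and two dependent measurements", "based on the partial eta squared (η^2) value of 0.108 obtained with a 0.05 error margin". With f² = 0.108/0.892 = 0.121, N = 28, two measurements and an assumed correlation of 0.5 (not in the documents), λ = 0.121 × 28 × 2/0.5 = 13.56. The noncentral F with (1, 26) df gives power 0.943, matching the stated 0.94. Other correlations give 0.71 (0), 0.85 (0.3) and 0.996 (0.7). So the statement can be reproduced, and Wong-Baker is its outcome.

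**Count of p-values.** Tables 1 to 5 print 4, 8, 8, 12 and 6; the correlations add 8. Total 46, of which 10 are at or below 0.05.

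**Four pain tests (Table 2; group sizes 6+3 = 9 and 12+7 = 19 from Table 3).**

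| Scale | Sequence | NF − TM | p |
|---|---|---|---|
| Wong-Baker | NF-TM | 4.44 − 1.55 = +2.89 | 0.056 |
| Wong-Baker | TM-NF | 2.52 − 1.68 = +0.84 | 0.119 |
| FLACC | NF-TM | 0.78 − 0.11 = +0.67 | 0.141 |
| FLACC | TM-NF | 0.68 − 0.21 = +0.47 | 0.025 |

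Holm over these four: 4 × 0.025 = 0.100, so none is significant.

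**Declared secondary results, Holm within family.** The printed 0.000 is entered as 0.0005.
- Eight correlations: 8 × 0.0005 = 0.004 passes; 7 × 0.009 = 0.063 fails; 6 × 0.033 = 0.198 fails.
- Table 5, six tests: 6 × 0.008 = 0.048 passes; 5 × 0.012 = 0.060 fails.

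**One cross-over comparison per scale.** Table 2 states that paired t-tests were used, so the SD of the within-child differences is |difference| × √n / t, with t taken from the printed p (two-sided assumed).
- Wong-Baker: 2.89 × 3/2.233 = 3.88 and 0.84 × √19/1.637 = 2.24.
- FLACC: 0.67 × 3/1.634 = 1.23 and 0.47 × √19/2.445 = 0.84.

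The technique effect is the mean of the two sequence differences.
- Wong-Baker: (2.89 + 0.84)/2 = 1.865.
  - Pooled variance: (8 × 3.88² + 18 × 2.24²)/26 = 8.10, SE = ½√[8.10 × (1/9 + 1/19)] = 0.576, t = 3.24 on 26 df, p = 0.003, 95% CI 0.7 to 3.0.
  - Unequal variances: SE = ½√(3.88²/9 + 2.24²/19) = 0.696, t = 2.68 on about 10.6 df, p = 0.022, CI 0.33 to 3.40.
- FLACC: (0.67 + 0.47)/2 = 0.57.
  - Pooled: SE 0.197, t = 2.89, p = 0.008, CI 0.16 to 0.98.
  - Unequal variances: SE 0.226, t = 2.52 on about 11.7 df, p = 0.028.

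**The case against.** The strongest reply is that multiplicity is not the main problem. If the cross-over rebuild is right, FLACC p=0.025 is not a false positive; the larger error is two missed Wong-Baker differences. Naming FLACC as primary would still leave 0.141 against 0.025, and correcting alpha moves further from the answer. This stands, and it is why the remedy must be a combined comparison and not only an adjusted threshold.

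Several stronger readings are tempting but not supported:
- A reader might infer that the four pain results contradict one another. They agree in direction; three labels against one differ. Wong-Baker alone gives the same label twice.
- A reader might take 46 × 0.05 = 2.3 as the expected number of false positives. Fourteen of the 26 subgroup Wilcoxon tests have N≤4, where the smallest asymptotic p is 0.068, and the gender row of Table 1 is p=1 by design. That leaves 31 tests, or about 1.55 if every null held. For the four pain tests, family-wise error is 1 − 0.95⁴ = 18.5% under independence, but only 1 − 0.95² = 9.8% if the two scales were perfectly correlated; the Results report them as correlated.
- A reader might infer that the subgroup tables are full of stray positives. All 20 tests in Tables 3 and 4 are reported as non-significant, and the two positives in Table 5 agree with the overall volume result for that sequence (p<0.0001).
- A reader might call the FLACC-volume correlation a chance finding. Table 2 shows higher FLACC and lower volume with NF in both sequences, so if techniques were pooled (the text does not say), technique alone could produce it. No alpha correction repairs that.

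Which results fail also depends on the method and family. Benjamini-Hochberg over the eight Table 2 tests keeps FLACC (0.025 × 8/5 = 0.040), and within their families it keeps Table 5 p=0.012 (0.012 × 6/2 = 0.036) and the correlation at 0.009 (0.009 × 8/2 = 0.036). Finally, front matter is not in the reviewed text, so a primary outcome named only there cannot be excluded; the analysis section does not apply one.

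**Conclusion.** The point holds in this form: a flat rule without a visible primary outcome, applied within sequence groups of 9 and 19, leaves the pain question without a single answer. Analysed as one cross-over comparison, both scales suggest more pain with NF: about +1.9 on Wong-Baker and +0.57 on FLACC, with p below 0.05 whether variances are pooled or not. That would probably change the reported Wong-Baker conclusion.

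The lesser part is that the correlations at p=0.009 and 0.033 and the Table 5 result at p=0.012 do not survive Holm in their own families, with the dependence on family noted above.

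The rebuilt figures rest on rounded means and p-values, two-sided paired t-tests, approximate normality of the differences and no carry-over between visits. The Wong-Baker difference SDs are unequal, with the larger in the smaller group, so 0.022 is the safer of the two p-values. They show what the raw-data analysis is likely to find and do not replace it.

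**What to change.** - **Primary.** Name Wong-Baker, the outcome in the plan's own power statement, with one two-period cross-over comparison of NF and TM over all 28 children, run on the raw data and allowing for unequal variances. Report the estimate with its confidence interval.
- **Secondary.** Analyse FLACC, volume and duration in the same way, with Holm over the three.
- **Exploratory.** Present Tables 3 to 5 and the correlations without significance claims. For the correlations, say whether the two techniques were pooled.
- **Disclosure.** State that this hierarchy was set after the data were seen.

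No new data are needed: the work is revised wording, one model per outcome and relabelled tables. The cost is in the conclusions. The reported absence of a significant Wong-Baker difference would probably be reversed, and a few secondary claims would lose their significance label.

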3.3 Procedure

The study was conducted by two expert pediatric dentists. One of them gave all explanation, spoke with the children and carried out the anesthesia procedure and did the treatment procedure [name] and the other [name] was observing and assessing the children's pain perception.

In this study's cross-over design, children received both types of injections before filling/pulpotomy treatment on their maxillary primary molars in two separate appointments with a minimum interval of at least 1 week between procedures, on a side of the dental arch with the use of a needle free injection and on the other side with the traditional syringe. Type and sequence of administration to each individual were randomly assigned (using a coin). All dental equipment were introduced using 'tell-show-do technique. A total of 56 procedures were performed and divided into 2 groups according to the anesthesia technique. None of the children have undergone any previous dental local anesthetic experience, in order to be not influenced by a positive or negative memory.

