3.3.1 Injection with the needle-free (NF) system

The device used for needle free system was **Comfort-in™** (Mika Medical Global Co, Busan, Korea) anesthesia device (Figure 1). The **Comfort-in™ system**, has a micro-hole injection needle (0.15 mm) that injects the anesthetic solution under the mucosa. The pressure can be controlled according to the dose of the drug to be used, thereby reduced the pain that may occur with the needle in the injection. Before the injection procedure, the children were demonstrated the popping sound produced by device to prevent reflex reactions, and they informed that they would feel as if their gum were punched. The NF injection device was prepared according to the manufacturer's instructions, placed in full contact with the buccal mucosa and a pre-withdrawn dose of 0.1 ml was applied to the buccal region for topical purposes by the pushing the top of the device. After 10-15 seconds, the same procedure was repeated with withdrawn dose of 0.3 ml. After 5 min the treatment commenced, and the children were instructed to raise their hand if they experienced pain during the procedure. Each time the child indicated pain, in accordance with the same protocol an additional 0.3 ml of anesthetic solution was administered, until the sufficient anesthetic effect was obtained and the final amount of anesthetic solution

The Effect of Needle-free Injection System on Dental Injection Pain in Children: A Cross-over, Randomized Clinical Trial

were recorded. Precautions were taken to prevent tissue ballooning. After the treatment, duration of the analgesia effect (min) were also recorded. The presence of post-operative pain in patients was assessed via a phone call 1 day after the procedure.

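### One-day post-operative pain is a paired outcome, but Table 1 lists it beside gender, tooth type and treatment type, tests it as unpaired, and reports only a non-significant p-value without an effect estimate or interval.

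*Combined protocol and SAP*

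**What the plan says.** - **Design.** Section 3.3: "children received both types of injections before filling/pulpotomy treatment on their maxillary primary molars in two separate appointments". Each child therefore contributes one observation under each technique.
- **Collection.** Section 3.3.1: "The presence of post-operative pain in patients was assessed via a phone call 1 day after the procedure". Section 3.3.2 says the same for the traditional method. It is item 7 on the form in section 3.4, the only item recorded after the treatment day. No adverse-event item is listed.
- **Analysis rule.** Statistical Analysis: "The Chi-square test (X^2 -test) was also used to compare discrete random variables", and "A p-value ≤ 0.05 was considered statistically significant". The Table 1 footnote repeats the chi-square statement.
- **Result.** Section 4 reports "a total of 56 injections were obtained for 28 children as NF injection (n = 28) and TM injection (n = 28"). The Table 1 row labelled "Post-op pain (after one day") shows pain in 5 and no pain in 23 for NF, pain in 7 and no pain in 21 for TM, p=0.746. The text groups this row with gender, treatment type and tooth type and concludes: "it was found that there was no statistically significant difference between the groups. (Table 1").
- **Power.** The only power statement is post hoc: "the results of the comparison between the injection systems and Wong Baker scores were evaluated", giving 0.94. Nothing comparable is given for next-day pain.

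**The concern.** Pain the day after treatment arises after the injection, so it is an outcome. In Table 1 it is handled like a background characteristic: compared by p-value and covered by the sentence that also covers gender.

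Two things are lost. First, the two columns hold the same children, and an unpaired test discards that. Second, a p-value above 0.05 does not show which differences the data still allow. With 12 reports of pain in 56 procedures that range is wide, and it cannot be recovered from the printed margins because the number of children with pain after both techniques is not given. A reader comparing the techniques on next-day pain has only the two margins and a p-value.

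**Working it through.** **Inputs.** 28 children, each treated with both techniques (sections 3.3 and 4); pain 5/28 NF and 7/28 TM, p=0.746 (Table 1); significance level 0.05 (Statistical Analysis), taken as two-sided because no side is stated. The 20-point difference used in step 4 is my assumption.

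**1. The printed p-value.** For 5/23 against 7/21, unpaired:
- Fisher exact: 0.7458
- chi-square with Yates correction: 0.7447
- uncorrected chi-square: 0.5148

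The printed 0.746 is reproduced by Fisher's test, although the footnote names chi-square. All three treat the columns as independent.

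**2. The stated power.** f = sqrt(0.108/0.892) = 0.348. With N = 28, two measurements and an assumed correlation of 0.5, the noncentrality is 28 x 2 x 0.348^2/(1 - 0.5) = 13.6. On F(1, 26) this gives 0.943, matching 0.94. It describes Wong-Baker scores and does not carry over to a yes/no outcome.

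**3. What the paired data could show.** Let k be the number of children with pain after both techniques (0 to 5). Then 5-k had pain after NF only, 7-k after TM only, and 16+k after neither. The difference is 5/28 - 7/28 = 17.9% - 25.0% = -7.1 points for every k.

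Exact McNemar: p = 2 x P(X <= 5-k), X ~ Binomial(12-2k, 0.5).

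Newcombe paired interval, with Wilson limits l and u (NF 7.9% to 35.6%, TM 12.7% to 43.4%):
- phi = [k(16+k) - (5-k)(7-k)] / sqrt(5 x 23 x 7 x 21)
- lower = d - sqrt[(p1-l1)^2 - 2 phi (p1-l1)(u2-p2) + (u2-p2)^2]
- upper = d + sqrt[(u1-p1)^2 - 2 phi (u1-p1)(p2-l2) + (p2-l2)^2]

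For k = 0, phi = -35/130.0 = -0.269 and lower = -0.071 - sqrt(0.0998^2 + 2 x 0.269 x 0.0998 x 0.1836 + 0.1836^2) = -0.303.

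| k | phi | McNemar p | 95% CI, NF minus TM (points) |
|---|---|---|---|
| 0 | -0.27 | 0.774 | -30.3 to +17.0 |
| 1 | -0.05 | 0.754 | -28.5 to +15.0 |
| 2 | 0.16 | 0.727 | -26.6 to +12.8 |
| 3 | 0.38 | 0.688 | -24.4 to +10.2 |
| 4 | 0.59 | 0.625 | -22.0 to +7.3 |
| 5 | 0.81 | 0.500 | -19.0 to +3.5 |

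Every upper limit is below +20. The lower limit passes -20 for k = 0 to 4 and stops just short at k = 5. That last case is borderline: with Newcombe's continuity correction to phi it becomes -20.6 to +5.5. The unpaired Newcombe interval is -28 to +14.

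**4. Chance of missing an assumed 20-point difference at n = 28.** Exact enumeration, two-sided 0.05; phi is the within-child correlation.

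| Rates | Fisher | McNemar, phi 0 | phi 0.3 | phi 0.5 |
|---|---|---|---|---|
| 25% vs 45% | 74% | 76% | 68% | 59% |
| 17.9% vs 37.9% | 71% | 73% | 65% | 56% |
| 25% vs 5% | 61% | 61% | 53% | not attainable |

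For 25% vs 5%, phi cannot exceed (0.05 - 0.25 x 0.05)/sqrt(0.25 x 0.75 x 0.05 x 0.95) = 0.40; at that ceiling exact McNemar misses about 50%. Uncorrected chi-square would miss 65%, 61% and 40% in the three rows, but it is not the test that produced the printed p-value.

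**The case against.** The sentence in section 4 is literally true, and the full counts are printed. A reader might infer that the documents declare the techniques equal or equally safe for next-day pain. They do not: the text reports only the absence of statistical significance, and the supplied text has no discussion or conclusion that goes further. That part of the objection stands, so this is a defect of analysis and reporting, not a false claim.

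Table 1 can also be read as the table of categorical variables, since Table 2 is titled as covering continuous ones. Its placement may be layout only. That is fair, but it does not explain the unpaired test or the missing interval.

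A reader might also infer that the study leaves a large difference open in both directions. Step 3 does not support this: for every possible paired table the upper limit is +17 points or less, so a 20-point excess with NF is excluded. At maximum overlap a 20-point excess with TM is also just excluded, or just not, depending on the version of the interval.

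The miss rate depends on an assumed difference, base rate, test and correlation, and no single narrow figure is defensible. Once data exist, the interval is the better measure.

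Finally, the documents never call this outcome a harm of the injection. It follows a filling or a pulpotomy, and Table 1 has 6 pulpotomies under NF and 14 under TM (p=0.051). A paired difference would not by itself isolate the technique.

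**Conclusion.** The point holds as a request for better analysis and reporting. Pairing does not make the result significant: exact McNemar gives p between 0.50 and 0.77 whatever the overlap. What changes is what can be concluded. The estimate is -7 points, with an interval between -30 to +17 and -19 to +4. The data are compatible with no difference and, for most possible tables, with an excess of more than 20 points under TM; they are not compatible with a 20-point excess under NF.

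For an assumed 20-point difference the miss rate is about 53-76% over the Fisher and exact McNemar cases shown, well above the 20% that a trial sized for 80% power would accept. This rests on two-sided testing, complete phone follow-up (the counts total 56), and a 20-point difference that the documents do not state. The outcome is secondary and its counts are disclosed, so the change is advisable, not critical.

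**What to change.** 1. Report post-operative pain with the outcomes, not beside gender and tooth type.
2. Print the by-child 2x2 table: pain after NF (yes/no) by pain after TM (yes/no).
3. Replace the unpaired test with exact McNemar, and give the paired risk difference with its 95% interval, naming the interval method.
4. Word the conclusion from that interval once it is known. For example: pain in 18% after NF and 25% after TM, difference -7 points, with the paired 95% interval and the differences it does and does not exclude.
5. State that the trial was not sized for this outcome and that the 0.94 refers to Wong-Baker scores.
6. State that pulpotomies were unequal. Check the counts first: Table 1 gives 6 NF and 14 TM, but the groups in Table 4 give 2 + 2 = 4 NF and 3 + 9 = 12 TM.

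The cost is one small table, one interval and a reworded sentence, from data already on the form. The downside is that the result will read as inconclusive.
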